4.2.8.3 Vital signs, physical examination and electrocardiogram

For vital signs data, descriptive statistics for absolute value, change from baseline and percent change from baseline will be presented for each treatment group by scheduled visit. Summary statistics for continuous variables will present n, mean, SD, Minimum, Q1, median, Q3, and Maximum.

For physical examination data, only information on whether the assessment was performed or not is to be recorded.

For ECG at screening, descriptive summaries of normal or abnormal evaluation and clinical significance will be provided by treatment group.

All vital sign and ECG data will be listed.

Vital signs and electrocardiogram data will be presented for both, the 16-week placebo-controlled treatment period and the Week 52 end of study reporting.

4.2.9 Tertiary/exploratory Endpoints

Analyses for exploratory objectives will be specified below, or additionally in an exploratory analysis plan.

4.2.9.1 Healthcare resource utilisation

Descriptive summary statistics will be produced by treatment group and visit.

4.2.9.2 Hospital Anxiety and Depression Scale (HADS)

The change from baseline in HADS scores for anxiety and depression, respectively, will be analyzed at Week 16 and at Week 52 using MMRM models as described for the change in EASI (Section 4.2.7.3).

Descriptive summary statistics for HADS anxiety and depression scores and change from baseline will be produced by treatment group and visit. Summaries of score categories considered normal, possible cases of anxiety/depression, and likely cases of anxiety/depression will be produced by treatment group and visit.

4.2.9.3 Patient Global Impression of Severity (PGI-S)

The PGI-S scores will be summarized descriptively by treatment group and visit for both, the 16-week placebo-controlled treatment period and the Week 52 end of study reporting.

4.2.9.4 SF-36 (Version 2), Acute Recall

The number and percentage of participants above and below the threshold values for the SF-36v2 Scale domains, PCS and MCS will be presented. The binary endpoints will be analyzed at Week 16 and at Week 52 using logistic regression models in a similar way to that described for the primary endpoint analyses (Section 4.2.6.1).

Descriptive summary statistics for scores and change from baseline will be produced by treatment group and visit.

CCI

CCI

4.2.9.6 Patient-reported Experience

The Patient-reported Experience will be analyzed separately and not form part of this SAP.

4.2.9.7 Body Surface Area Involvement of Atopic Dermatitis

The change from baseline body surface area involvement at Week 16 and at Week 52 will be analyzed using MMRM models as described for the change in EASI (Section 4.2.7.3). Both, the results from regular assessment and from electronic device calculations will be analyzed separately.

Descriptive summary statistics for scores and change from baseline will be produced by treatment group and visit.

4.2.9.8 European Quality of Life-5 Dimensions (EQ-5D-5L)

The EQ-5D-5L will be analyzed separately and not form part of this SAP.

CCI

4.2.9.11 Biomarkers

To explore the pharmacodynamic effect of benralizumab, summaries and plots of absolute levels and changes from baseline in pharmacodynamic biomarkers including CCI

will be produced as appropriate.

To evaluate the association of baseline biomarkers with clinical efficacy, and assess for any markers potentially predictive of benralizumab treatment effect the following analysis techniques may be considered:

- Forest plots for binary efficacy measures (primarily IGA response, EASI-75 response may also be included if necessary) at Week 16 of odds ratio by biomarker quartiles or clinically relevant thresholds pre-defined before unblinding;
- Scatterplots of baseline biomarker levels versus continuous efficacy measures (change from baseline for EASI, POEM and SCORAD) at Week 16, with locally weighted smoothing (LOESS) lines by treatment as appropriate;
- If appropriate, forest plots presenting subgroup analyses of continuous efficacy measures at Week 16 (eg change from baseline for EASI) by subgroups defined by baseline biomarker levels. Groupings of baseline biomarker levels may include splitting biomarkers at the median, at tertiles, or at quartiles, or other clinically relevant thresholds of interest to be pre-defined prior to unblinding. Results would be presented in forest plots of treatment effect (difference between benralizumab and placebo in change from baseline in EASI at Week 16) in each level of the biomarker subgroups.

Additional Biomarker analyses may be explored separately outside of this SAP.

4.2.9.12 Clinical skin photography

Results from clinical skin photography assessments will be compared to in-person assessments of clinical efficacy taken on the same visit. Descriptive summary statistics for clinical skin photography assessments of scores and change from baseline will be produced by treatment group and visit.

Agreement between skin photography and in-person clinical assessment will be explored over all treatment groups (benralizumab, placebo) combined, as follows:

For binary outcomes (IGA response) cross-tabulations of responder/non-responder by skin photography/in-person assessment will be produced, presenting number and percent in each category. Cohen's kappa statistic (κ) will be calculated for evaluating agreement:

$$\kappa = (\text{observed agreement } [Po] - \text{expected agreement } [Pe]) / (1 - \text{expected agreement } [Pe]),$$

where $Pe=0.5$.

The results will be interpreted as 0 = agreement equivalent to chance; 0.10–0.20 = slight agreement; 0.21–0.40 = fair agreement; 0.41–0.60 = moderate agreement; 0.61–0.80 = substantial agreement; 0.81–0.99 = near-perfect agreement; and 1.00 = perfect agreement.

For the continuous outcomes (EASI, SCORAD, BSA) Bland-Altman plots and limits of agreement (Bland and Altman 1986) will be used. Scatter plots will be produced of the difference between the two measurements (y-axis) against the average of the two

measurements (x-axis), and colour coded by time point. This provides a graphical display of bias with 95% limits of agreement (difference $\pm 1.96 \times$ SD of observed differences).

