3.2 Primary outcome variable

The proportion of participants with an Investigator Global Assessment (IGA) 0/1 and a decrease in IGA of ≥ 2 points at Week 16 relative to baseline will be used as the primary efficacy variable.

The IGA is an instrument used in clinical studies to rate the severity of AD globally, based on a 5-point scale ranging from 0 (clear) to 4 (severe). The IGA uses clinical characteristics of erythema, infiltration, papulation, oozing, and crusting as guidelines for the overall severity assessment. The validated IGA scale for AD will be completed by the Investigator on an electronic device supplied to the site according to the Schedule of Activities (SoA) (CSP Table 3) to capture these key measures of AD disease activity and describe the overall appearance of AD lesions (Table 4).

Table 4 Investigator Global Assessment Score

Score	Morphological description
0 – Clear	No inflammatory signs of atopic dermatitis (no erythema, no induration/papulation, no lichenification, no oozing/crusting). Post-inflammatory hyperpigmentation and/or hypopigmentation may be present.
1 -- Almost clear	Barely perceptible erythema, barely perceptible induration/papulation, and/or minimal lichenification. No oozing or crusting.
2 -- Mild	Slight but definite erythema (pink), slight but definite induration/papulation, and/or slight but definite lichenification. No oozing or crusting.
3 -- Moderate	Clearly perceptible erythema (dull red), clearly perceptible induration/papulation, and/or clearly perceptible lichenification. Oozing and crusting may be present.

Table 4 Investigator Global Assessment Score

Score	Morphological description
4 -- Severe	Marked erythema (deep or bright red), marked induration/papulation, and/or marked lichenification. Disease is widespread in extent. Oozing or crusting may be present.

A responder at Week 16 is defined as having IGA 0/1 and a decrease in IGA of ≥ 2 points at Week 16 relative to baseline.

In the statistical analyses, a binary variable will take on value 1 if a participant is defined as a responder, and value 0 for non-responder, and will be used as the response variable for the efficacy analysis.

Intercurrent events will be considered as described above in Section Intercurrent Events (Section 3.1.5). Intercurrent events will be considered for analyses and descriptive summaries.

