3.5.12 Clinical skin photography

Clinical skin photography is a method to capture and document images of the skin. To evaluate alternative methods of clinical assessments, skin photography will be used in this study. Full body photographs will be taken as outlined in the photography manual and according to the SoA (CSP Table 3). At visits when clinical skin photography is to be performed and assessed before the Investigator sees the participant for the study visit, the photographs should be taken by a trained site personnel and not by the Investigator performing efficacy assessments on the participant. The site Investigator will then review the photographs and perform the clinical efficacy assessments (IGA, EASI, SCORAD, and BSA) based on review of the photographs. The Investigator photograph assessment will be recorded in the electronic case report form (eCRF). The same site Investigator should then see the participant and perform the usual in-person visit assessments including the in-person assessment of efficacy parameters, and document the data. The first assessments (based on skin photography) should not be altered even if differences are observed after assessing the participant in person. The final in-person Investigator assessment documented should reflect

the Investigator's overall clinical judgment. Photographic equipment will be provided to the sites.

The clinical efficacy assessments (IGA, EASI, SCORAD, and BSA) are described for primary and secondary endpoints in Sections 3.2 and 3.3 above. For these exploratory analyses of agreement between the in person and photograph assessment, the total scores or matching sub-scores will be used.

All available data will be included, regardless of intercurrent events like taking rescue medication or withdrawal from study.

The photographic assessment results will be examined against the in-person assessment results at Week 16 analyses.

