4.2.6.2 Subgroup analyses for the primary outcome variable

To explore the uniformity of the detected overall treatment effect on the primary efficacy variable, subgroup analyses and statistical modelling including testing for interaction between treatment and covariates will be performed for the following factors:

- Region (Europe, North America, Rest of World)
- Gender (male, female)
- Age group categories (< 18 years, ≥ 18 – 35 years, ≥ 35 years) at screening from eCRF
- Age group categories (< 21 years, ≥ 21 – 35 years, ≥ 35 years) at screening from eCRF
- Blood eosinophils (< 300 cells/μL, ≥ 300 cells/μL) at screening from central laboratory results
- BMI ($\leq 30 \text{ kg/m}^2$, $> 30 \text{ kg/m}^2$)
- Race (White, Asian, Other)
- Duration of AD at enrolment (< median, ≥ median; calculated on FAS)
- Age at onset of AD (< 18 years, ≥ 18 years; if sufficient data: < 12 years, ≥12 – 18 years, ≥ 18 years)
- Baseline IGA score (3, ≥ 4)
- Baseline EASI (< median, ≥ median)
- Previous biologic use (yes, no; if sufficient data: responded to, failed, naïve) at screening from eCRF
- Previous immunosuppressant (yes, no; if sufficient data: responded to, failed, naïve) at screening from eCRF
- Co-morbid asthma (yes, no) at screening from eCRF
- IgE (< median, ≥ median) from central laboratory results; calculated on FAS
- Staph aureus (lesional) (yes, no)
- Staph aureus(non-lesional) (yes, no)
- Aeroallergens (yes, no) at screening from eCRF
- Food allergies (yes, no) at screening from eCRF

For each of the subgroup factors in turn, a separate logistic regression model will be fitted using the same model terms as used for the primary analysis (described in Section 4.2.6.1),

with additional terms for the subgroup main effect (unless the subgroup main effect is already included) and the treatment by subgroup interaction. If any model does not converge, respective sub-groups may be collapsed appropriately.

Similar outputs will be presented for each subgroup as for the primary analysis. The p-value for the interaction term by each treatment group will be presented in the analysis summary tables and forest plots will present the odds ratios with confidence intervals for each level of the subgroups.

It is important to note that the study has not been designed or powered to assess efficacy within any of these pre-defined subgroups (except for strata of age and eosinophils), and as such these analyses are considered as exploratory.

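### Paired photograph versus in-person agreement on IGA is assessed only as responder/non-responder, so disagreements within IGA 2–4, and 0 versus 1, count as agreement

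*SAP*

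**What the plan says.** SAP section 3.5.12 has the investigator rate IGA, EASI, SCORAD and BSA from photographs and then in person at the same visit. It continues: "For these exploratory analyses of agreement between the in person and photograph assessment, the total scores or matching sub-scores will be used".

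Section 4.2.9.12 gives the methods. For three of the four instruments, "For the continuous outcomes (EASI, SCORAD, BSA) Bland-Altman plots and limits of agreement (Bland and Altman 1986) will be used". For the fourth, "For binary outcomes (IGA response) cross-tabulations of responder/non-responder by skin photography/in-person assessment will be produced", followed by Cohen's kappa with expected agreement fixed at 0.5 and verbal bands for reading it. Treatment groups are combined. The section also plans unpaired output: "Descriptive summary statistics for clinical skin photography assessments of scores and change from baseline will be produced by treatment group and visit".

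Section 3.2 describes the IGA as "based on a 5-point scale ranging from 0 (clear) to 4 (severe") and sets the cut: "A responder at Week 16 is defined as having IGA 0/1 and a decrease in IGA of ≥ 2 points" relative to baseline. The subgroup list in section 4.2.6.2 gives the baseline categories as "Baseline IGA score (3, ≥ 4"), so on a scale ending at 4 the expected baseline values are 3 and 4.

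**The concern.** Section 3.5.12 points to an analysis of scores, and section 4.2.9.12 delivers one for EASI, SCORAD and BSA. IGA enters only after dichotomisation, and no paired analysis of the IGA score is planned: no 5×5 table, weighted kappa or exact agreement.

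The cut treats the five levels unevenly. With a baseline of 3 or 4, levels 2, 3 and 4 are all non-response. A pair graded 2 and 4 counts as full agreement, and a pair graded 1 and 2 as full disagreement. Pairs graded 0 and 1 also count as agreement when both readings meet the required drop. Response is defined relative to baseline, so a baseline pair cannot enter the table, and whether photographs separate IGA 3 from 4 at entry is not tested.

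The photography is there to evaluate an alternative way of making the clinical assessments. For the instrument behind the primary endpoint, the planned statistic could look excellent while photographs systematically under-grade moderate and severe disease.

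**Working it through.** **Inputs from the SAP.** Section 1.2 assumes response rates of 40% and 10% with at least 80 participants per group. Pooled response is (0.40 + 0.10)/2 = 25%, so 75% of pairs are expected in the range where the cut does not discriminate. The SAP states no sample size or precision for the agreement analysis, so there is no figure of its own to reproduce.

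**Assumptions, not in the SAP.** 160 pairs at one visit; the IGA distributions below; a latent correlation of 0.9 between the two readings in steps 3 and 4.

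**1. What the cut can miss.** Take in-person IGA 0–4 as 8/17/25/32/18%, which gives 25% at 0/1. On photographs, half of the 4s are read as 3 and 40% of the 3s as 2.
- Misgraded pairs: 0.5 × 0.18 + 0.4 × 0.32 = 0.090 + 0.128 = 0.218.
- Exact agreement: 1 − 0.218 = 78% overall; 1 − 0.218/0.75 = 71% among those at IGA 2–4.
- No pair crosses between 0/1 and 2–4. With the in-person baseline for both readings, observed agreement Po = 1 and kappa = (1 − Pe)/(1 − Pe) = 1.00 for any expected agreement Pe.

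**2. The same error in photograph baselines.** Response also needs a drop of 2 points. A participant with true baseline 3 read as 2, and a later score of 1, is then a photograph non-responder. Let f be the share with true baseline 3, unrelated to response. The share of in-person responders lost is f × 0.40 × 0.17/0.25 = 0.272f.
- f = 0.5: 13.6% lost; Po = 1 − 0.25 × 0.136 = 0.966. Kappa is 2 × 0.966 − 1 = 0.93 with Pe = 0.5. With marginal Pe = 0.25 × 0.216 + 0.75 × 0.784 = 0.642, it is 0.324/0.358 = 0.91.
- f = 0.7: 19.0% lost; Po = 0.952. Kappa is 0.90 with Pe = 0.5, or 0.86 with marginal Pe = 0.649.

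**3. Random rather than systematic error.** Assume levels 7/18/27/33/15% and cut a bivariate normal with correlation 0.9 at those margins for both readings. Pairs that differ in level: 37.6% of 160, about 60. Of these, 58% lie within IGA 2–4 and 12% are 0 versus 1, so about 0.70 × 60 = 42 are hidden by the cut.

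**4. Precision in that setting.** Half-width = 1.96 × asymptotic standard error. For fixed Pe = 0.5 the standard error is 2√(Po(1 − Po)/n) = 2√(0.886 × 0.114/160) = 0.050.

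| Statistic | Kappa | 95% half-width |
|---|---|---|
| Binary, Pe = 0.5 (SAP) | 0.77 | 0.10 |
| Binary, marginal Pe | 0.70 | 0.13 |
| Five-level, unweighted | 0.50 | 0.10 |
| Five-level, linear weights | 0.69 | 0.07 |
| Five-level, quadratic weights | 0.84 | 0.05 |

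**5. What the replacement shows in step 1.** The mean squared level difference is 0.218. Under independence it is the two variances plus the squared mean difference: 1.408 + 1.115 + (2.350 − 2.132)² = 2.570. Quadratic-weighted kappa = 1 − 0.218/2.570 = 0.92. With linear weights it is 1 − 0.218/1.260 = 0.83. Both are still high. The shift is exposed by the 5×5 table itself, where every discrepant pair lies on the same side of the diagonal.

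**The case against.** The trial uses IGA as a responder endpoint, and whether photographs reproduce that classification is a fair question that a 2×2 table answers directly. A weighted kappa answers a different one. The analysis is exploratory, with no decision rule attached. This stands, and is why the responder table should stay.

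The sentence in section 3.5.12 may have been written with the composite instruments in mind, since IGA is a single rating without sub-scores. That softens the mismatch. But IGA is named in the same paragraph, and responder status is not its score.

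EASI, SCORAD and BSA are compared on continuous scales, and photograph scores are summarised by visit. In the step 1 example the share at IGA 4 falls from 18% to 9%, so a shift that large might surface there. Those outputs concern other instruments or are unpaired, and do not test IGA agreement.

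A reader might infer that the responder cut throws away most of the precision. The SAP gives no figure for this, and the answer depends on the assumed distribution, the correlation and the comparator. At correlation 0.9 an unweighted five-level kappa is no more precise than the planned fixed-Pe kappa. The coefficients also measure different things, so their half-widths are not strictly like for like. A reader might also infer that such misgrading would always be reported as perfect agreement. That holds in the example only if the in-person baseline is used or photograph baselines are read without the error. The SAP does not say which baseline applies.

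**Conclusion.** The point holds in a limited form. Paired IGA agreement is examined only on the responder cut, which sits poorly with section 3.5.12 and cannot register disagreement within IGA 2–4 or, in general, between 0 and 1. This follows from the text and needs only a baseline IGA of 3 or 4. Its size rests on assumptions: in the example, 22% of pairs are misgraded while the planned kappa is 1.00, or about 0.86–0.93 if photograph baselines carry the same error. The precision gain from a weighted kappa is a secondary benefit under the stated assumptions. Only the exploratory photograph comparison is affected; the efficacy analyses are not.

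**What to change.** In section 4.2.9.12, add the 5×5 cross-tabulation of photograph IGA by in-person IGA at each photographed visit, arms combined, with a weighted kappa and 95% CI. Name the weights in advance. Keep the responder/non-responder table for the responder question, and state which baseline defines photograph response. This also aligns the section with 3.5.12.

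The cost is SAP wording and one extra table from data already recorded. The verbal kappa bands do not carry over directly to a weighted kappa, so the text should say they apply to the responder table only, and the 5×5 table should be read alongside the coefficient.

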1.1 Study design

1.1.1 Overall Design

This is a Phase 2 multinational, randomized, double-blind, parallel-group, 16-week placebo-controlled study with a 36-week extension. The study will evaluate the efficacy and safety of benralizumab 30 mg in male and female participants ≥ 12 years of age with moderate to severe atopic dermatitis (AD) who remain symptomatic despite treatment with standard of care treatment with topical medications. At this time adolescent participants will not be enrolled in sites in the United States. Adolescents may be recruited when and where approval is granted. The study is designed to assess the safety and efficacy of benralizumab 30 mg compared with placebo and identify the appropriate maintenance administration frequency (every 4 weeks (Q4W) versus every 8 weeks (Q8W)).

This study consists of the following consecutive periods:

- A 1- to 4-week run-in period, including a 7-day washout period of topical medications prior to randomization;
- A 16-week placebo-controlled, double-blind treatment period;

- A 36-week blinded-to-dosing regimen extension period for maintenance treatment.

[figure not shown]
Following informed consent, all eligible participants will enter a run-in period of 1 to 4 weeks during which inclusion/exclusion criteria will be assessed, medical history taken, and complete physical exam will be conducted (Visit 1, CSP Table 3). Potentially eligible participants will enter a 7-day washout period during which all topical medications for AD except the stable emollient moisturizer regimen must be discontinued. Participants will be provided with a handheld device to respond to patient-reported outcome (PRO) questionnaires during the study.

Following the 1- to 4-week run-in period, including the 7-day washout period, a minimum of approximately 160 participants will be randomized at Visit 2, in a ratio of 1:1:2, respectively, to 1 of the following 3 treatment sequences (see also [Figure 1](#) and [Figure 2](#)):

- Benralizumab 30 mg Q4W until Week 16, followed by an extension period with benralizumab 30 mg Q4W administered until Week 52 (n = 40);
- Benralizumab 30 mg Q4W until Week 16, followed by an extension period with benralizumab 30 mg Q8W administered until Week 52 (n = 40);
- Placebo Q4W until Week 16, followed by an extension period with benralizumab 30 mg Q4W administered until Week 28, and then benralizumab 30 mg Q8W administered until Week 52 (n = 80).

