1.2 Number of participants

Approximately 270 participants are expected to be enrolled/screened in order to achieve at least 160, and a maximum of 200, eligible study participants randomly assigned to study intervention to ensure that a broad distribution of participants is recruited across the range of ages and blood eosinophil levels to allow potential identification of responding subpopulations and appropriate cut-offs for future studies, if necessary.

Randomization will be stratified by blood eosinophils (< 300 cells/ μ L, ≥ 300 cells/ μ L) collected at screening and age at screening (≥ 12 to < 18 years and ≥ 18 years). Participants will be randomized in minimum cohort sizes across the baseline blood eosinophil and age subgroups; the intended distribution of participants in total across the treatment groups for each combination of these factors is summarized in Table 2. If the minimum recruitment target in any cohort is achieved, that cohort may remain open in order to fulfil minimum recruitment targets for the remaining cohorts. Thus, minimum recruitment targets may be exceeded in cohorts that remain open while fulfilling recruitment targets for other cohorts. Recruitment will stop when a maximum of 200 participants in total is achieved.

Table 2 Number of Participants Randomized by Stratification Factors

	Baseline blood eosinophils	
	<300 cells/ μ L	\geq 300 cells/ μ L
Adolescents (\geq 12 to < 18 years), n	20	30
Adults (\geq 18 years), n	40	70

For the primary analysis in the overall population, a minimum of 80 participants per treatment group will provide a high level of power (> 95%) to detect a 30% difference between benralizumab 30 mg Q4W and placebo for the primary endpoint. This calculation is based on a 2-sided test and a 5% significance level and assumes a response rate of 40% for benralizumab 30 mg Q4W and 10% for placebo.

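### The statistic called Cohen's kappa for photograph versus in-person IGA response fixes expected agreement at 0.5, so it overstates agreement when responders are a minority

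*SAP*

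**What the plan says.** SAP section 4.2.9.12 (Clinical skin photography) compares photograph-based with in-person assessments. The population is pooled: "Agreement between skin photography and in-person clinical assessment will be explored over all treatment groups (benralizumab, placebo) combined". For IGA response, "cross-tabulations of responder/non-responder by skin photography/in-person assessment will be produced", and "Cohen's kappa statistic (κ) will be calculated for evaluating agreement".

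The formula given is kappa = (Po - Pe)/(1 - Pe), with Po the observed and Pe the expected agreement. A line beneath it sets Pe to 0.5. The reading of the result follows: "The results will be interpreted as 0 = agreement equivalent to chance", then a graded scale that includes "0.21–0.40 = fair agreement; 0.41–0.60 = moderate agreement; 0.61–0.80 = substantial agreement", with slight below these bands and near-perfect above them.

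Section 3.5.12 places the comparison at the Week 16 analyses. Section 1.2 "assumes a response rate of 40% for benralizumab 30 mg Q4W and 10% for placebo" for the primary endpoint, which is the same IGA response. The SAP gives no reason for 0.5 and names no other agreement coefficient for the binary outcome.

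**The concern.** Three statements in the section do not fit together: the name of the statistic, the fixed Pe, and the reading of zero as chance. Cohen's kappa corrects observed agreement for the agreement that two unrelated readings with the same margins would reach. When most participants are non-responders, that chance agreement is well above one half, because both readings are usually *non-responder* whatever the photographs show. A fixed Pe of 0.5 leaves this excess in the numerator and counts it as real agreement.

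Section 3.5.12 gives the purpose of the photography as evaluating alternative ways of making the clinical assessments. Kappa is the only agreement coefficient planned for IGA response, the measure behind the primary endpoint. A wrongly scaled kappa, read against verbal bands, could therefore make the photographs look more reliable than the data support. It also leaves the programmer to choose between standard software output for Cohen's kappa and the prespecified formula, and the two will differ.

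**Working it through.** **Inputs**
- Pe = 0.5, the reading of zero, and the bands: section 4.2.9.12.
- Response rates 40% and 10%: section 1.2.
- Allocation "in a ratio of 1:1:2" (section 1.1.1). The two benralizumab sequences share one regimen to Week 16, so the comparison is 80 versus 80.
- Photograph margins: not given. I take them as equal to the in-person margins and vary this below.

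**Where 0.5 can come from.** With k = 2 categories and uniform guessing, Pe = 1/k = 0.5. That is the chance model of Bennett's S, also known as the prevalence- and bias-adjusted kappa. It is not the chance model of Cohen's kappa.

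**Cohen's Pe.** With responder margins p1 and p2:

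Pe = p1·p2 + (1 - p1)(1 - p2), so Pe - 0.5 = (1 - 2·p1)(1 - 2·p2)/2.

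This difference is zero only if p1 or p2 is 50%.

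**Planned pooled rate.** (80 × 0.40 + 80 × 0.10)/160 = 40/160 = 0.25. With both margins at 0.25, Pe = 0.0625 + 0.5625 = 0.625.

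**What the SAP formula becomes.** (Po - 0.5)/0.5 = 2Po - 1. For independent readings Po equals the true Pe, so with equal margins p the SAP value is (1 - 2p)². Cohen's kappa is 0 in every row.

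| Responders, both readings | True Pe | SAP value under chance | SAP band |
|---|---|---|---|
| 40% | 0.520 | 0.04 | none assigned |
| 30% | 0.580 | 0.16 | slight |
| 25% (planned) | 0.625 | 0.25 | fair |
| 20% | 0.680 | 0.36 | fair |
| 15% | 0.745 | 0.49 | moderate |
| 10% | 0.820 | 0.64 | substantial |

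**Check with counts.** Take 160 participants with 40 responders by each method and independent readings. The cells are 10, 30, 30 and 90. Po = (10 + 90)/160 = 0.625 and Pe = (40 × 40 + 120 × 120)/160² = 0.625. The SAP value is 0.25; Cohen's kappa is 0.

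**Unequal margins.** For 25% and 20%, Pe = 0.05 + 0.60 = 0.65 and the SAP value under chance is 0.30. For 10% and 15%, Pe = 0.015 + 0.765 = 0.78 and the value is 0.56.

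**Real agreement above chance**

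| Responders, both readings | Po | SAP value | Cohen's kappa |
|---|---|---|---|
| 25% | 0.85 | 0.70 (substantial) | (0.85 - 0.625)/0.375 = 0.60 (moderate) |
| 10% | 0.85 | 0.70 (substantial) | (0.85 - 0.82)/0.18 = 0.17 (slight) |
| 10% | 0.90 | 0.80 (substantial) | (0.90 - 0.82)/0.18 = 0.44 (moderate) |

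**Where it matters.** Solving (1 - 2p)² = c gives p = (1 - √c)/2. Chance alone reaches fair (0.21) at about 27% responders or fewer, moderate (0.41) at about 18%, and substantial (0.61) at about 11%. Above about 34% the chance score is below 0.10.

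**The case against.** The strongest counter-argument is that 2Po - 1 is a recognised coefficient. Its zero is chance under uniform guessing, and some analysts prefer it because Cohen's kappa is pulled down when one category dominates. On that view, 0.17 at 10% responders is not obviously a better description than 0.70. This would carry weight if the SAP had named and justified that index. It names Cohen's kappa instead and applies the kappa bands, so the text needs correcting whichever index was meant.

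Other points limit the weight of the finding, and they stand:
- The analysis is exploratory and outside the testing hierarchy of section 4.1.1. EASI, SCORAD and BSA agreement is handled by Bland-Altman methods, which are unaffected.
- Under section 3.5.12 the same investigator makes both readings at the same visit. Independent readings are therefore a limiting case that shows where the zero lies, not an expected result. At the planned 25% and 85% agreement the practical effect is one band.
- The substantial grade under chance needs a pooled response near 10%, meaning benralizumab responds no better than the assumed placebo rate.
- The cross-tabulation will be reported, so a reader could recompute kappa.

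**Conclusion.** The concern holds. The rule as written is not Cohen's kappa, and zero on its scale is not chance agreement unless at least one reading has 50% responders. When both readings have fewer than 50% responders, the error always favours the photographs (short of perfect agreement), and it grows as response falls. At the SAP's planned pooled rate of 25% it adds 0.25 under pure chance and 0.10 at 85% agreement. At 10% it adds 0.64 and 0.53 (0.70 - 0.17).

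These sizes assume equal margins, but the direction does not depend on that. They also assume that the planned rates carry over. Those rates are for the primary endpoint, which counts rescue use and missing data as non-response, whereas section 3.5.12 uses all available data for the agreement analysis, so the response rate there may differ. No primary, key secondary or safety result is touched. The correction should still be made, because it changes both the reported value and its verbal grade.

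**What to change.** In section 4.2.9.12, delete the fixed value and define Pe from the observed margins of the planned cross-tabulation: Pe = p1·p2 + (1 - p1)(1 - p2), with p1 and p2 the proportions of responders by photograph and in person. State that kappa is reported with a 95% CI, in line with the general rule for point estimates in section 4.1. If the sponsor also wants an index that does not depend on prevalence, report 2Po - 1 beside kappa under its own name (Bennett's S, or prevalence- and bias-adjusted kappa), without the kappa bands or the reading of zero as chance.

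The cost is one line of SAP text. It needs no new data, and standard software already produces the statistic. The reported agreement will probably look less favourable.
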